### **6.3.2. Blinding**

Due to the nature of the study it will be impossible to blind either participants or therapists to study condition. We will make every effort to keep research assistants (RA) completing the follow up assessments blinded to study condition. The RA will instruct participants at the start of follow up assessments they are not to know which groups the client attended and will

request they not divulge it during the assessment. In addition the counselor or site coordinator will complete the study assignment line on any AE/SAE form the RA is required to complete.

### **6.3.3. Quality Control of Therapies Administered**

Since therapists will be trained to deliver both interventions there is a concern of contamination of the HIV Education control condition with material from the REMAS intervention. In addition there is the possibility REMAS material might be delivered to HIV Education participants by the therapists in individual counseling or other group therapy sessions. Finally REMAS participants may deliver the material indirectly to HIV Education participants in their contacts that are beyond the control of the investigators. Five procedures will be in place to maintain quality control of the therapies. 1) The design of the HIV Education session leaves little room to add additional information, and there is no time for role plays and brainstorming that characterizes the REMAS condition. 2) Both interventions will be manual driven, and the therapists will receive approximately 20 hours of training in conducting the interventions. 3) Therapists will complete an intervention checklist at the end of each session where they indicate whether each topic and activity for the session was covered. 4) All intervention sessions will be audio taped. 5) Participants will complete a fidelity questionnaire at each follow up assessment to determine if they have been exposed to elements of both the intervention to which they were assigned and not assigned.

One option the protocol development team considered to lessen the potential of contamination was to have separate therapists for each intervention condition. This option was rejected because it may introduce a larger problem of interventionists' effects. Najavits, Crits-Christoph and Dierberger (2000) provide an excellent review of this literature. The following quote highlights the potency of therapists' effects. "Ironically, however, clinicians typically account for *more* variance in patient outcomes than do differences between active treatments or patient baseline characteristics, a result which holds both in the substance abuse disorder field and psychotherapy research in general." In addition smaller CTPs may have difficulty identifying enough interventionists to be trained. Separate interventionists would not prevent the other types of contamination mentioned above, and the planned fidelity checks would still need to be implemented.

## **7.0 CONCOMITANT THERAPY**

### **7.1 General Considerations**

During part or all of the time participants are participating in the trial they will be engaged in their substance abuse treatment. As part of their treatment, there may be discussions about HIV risk behaviors that come up in groups or individual sessions. It would be unfeasible to prevent these from happening during the trial. Participants will be asked about exposure to such events on the fidelity measure. Also during the trial participants may have contact with other HIV prevention interventions such as media campaigns and street outreach efforts. Again it would be unfeasible and unethical to try and prevent these from happening during the trial, and we will be asking about these possibilities on the fidelity measure.

### **7.2 Therapies Prohibited During the Trial**

No concomitant therapies are prohibited during the trial. Therapists providing the communication skills and sexuality workshop will be instructed not to bring the interventions unique to the workshop into individual sessions during the trial. Participants will be asked about such exposures on the fidelity measure.

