## **6.2 Selection and Training of Therapists**

Therapists will be recruited initially from the counseling staff of the CTP sites. Priority will be given to those with group therapy and HIV prevention education experience. Two therapists will be trained for each site. Should there not be two counselors available or interested in conducting the interventions, the node project coordinator for the study will recruit and hire potential therapists from the community at large. Study counselors will receive approximately 20 hours of training in providing the interventions. The interventions are manual driven. The intervention expert and author of the TOMen and HIV-ED interventions, [name], and the lead investigator will conduct training. In addition, [name], a trainer from PL and member of the Northern New England Node, has joined the Protocol Development team and will consult with the training team.

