The second potential threat to intervention integrity is contamination between the interventions. Since the HIV/AIDS Education material is a subset of the REMAS intervention there is not a concern regarding HIV Education material contaminating the REMAS intervention. However there is a concern that HIV/AIDS Education participants may be exposed to REMAS intervention material in one of three ways. Since therapists will be trained to deliver both interventions there is a concern that the therapists will deliver REMAS unique materials when providing the HIV/AIDS Education intervention. Participants in the REMAS intervention group will share REMAS unique material to HIV/AIDS Education group participants. Finally HIV/AIDS Education participants may be provided REMAS unique material from sources the investigators will not be in a position to control. These include media, campaigns, street outreach workers and substance abuse counselors not associated with the study. Both of the procedures described above will help to lessen contamination problems (audio taping and supervision). Three additional procedures will be in place to maintain the integrity of the interventions. The design of the HIV/AIDS Education session leaves little room to add additional information, and there is no time for role plays and brainstorming that characterizes the REMAS condition. At the end of each session interventionists will complete a checklist of the topics and activities to be covered in the session. To further ensure integrity, however, study participants will be asked to complete an intervention fidelity questionnaire at post-intervention and at each follow up assessment to determine if they have been exposed to elements of both the intervention to which they were assigned and not assigned.

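### The protocol names other group therapy sessions as a way study therapists could pass REMAS material to control men, but its only restraining instruction covers individual sessions

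*Protocol*

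**What the plan says.** Both arms are run by the same counselors, and the protocol acknowledges the consequence in section 6.3.3: "Since therapists will be trained to deliver both interventions there is a concern of contamination of the HIV Education control condition". The same section adds a second worry, about settings outside the study sessions: "REMAS material might be delivered to HIV Education participants by the therapists in individual counseling or other group therapy sessions".

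It then lists five procedures: a tightly filled control session, manuals with about 20 hours of training, an end-of-session checklist, taping ("All intervention sessions will be audio taped"), and a participant fidelity questionnaire, which is meant "to determine if they have been exposed to elements of both the intervention to which they were assigned and not assigned".

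Section 7.2 prohibits no concomitant therapy, but says that therapists giving the workshop "will be instructed not to bring the interventions unique to the workshop into individual sessions during the trial". Nowhere else does the protocol tell study therapists to keep workshop material out of their ordinary clinical work.

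On who the therapists are, section 6.2 says "Therapists will be recruited initially from the counseling staff of the CTP sites" and "Priority will be given to those with group therapy and HIV prevention education experience". Community hires are allowed if two counselors cannot be found.

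**The concern.** The written concern has two branches, individual counseling and other groups. The written instruction has one. No reason is given for leaving groups out.

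The gap deserves attention for three reasons:

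- **Shared setting.** Cohorts are randomized within each treatment program (section 11.3), so men of both arms attend the same clinic.
- **Shared therapists.** Section 6.3.3 considers and rejects separate therapists for each arm. That makes the instruction to the shared therapists the main preventive measure outside study sessions.
- **Intent-to-treat analysis.** The primary analysis includes all randomized men as assigned (section 11.6). Learning later that control men were exposed does not restore the primary comparison.

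If control men did receive workshop material this way, the control arm would move toward REMAS and the estimated difference would shrink toward zero. Section 11.3 assigns its enrolment margin to attrition, recruitment difficulty and an underestimated intracluster correlation. Contamination is not among the reasons listed.

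**Working it through.** **Step 1: set each safeguard against the group route.**

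| Safeguard | Where | Does it restrain study therapists in other groups? |
|---|---|---|
| Full control-session timetable | 6.3.3 | No; concerns the control session itself |
| Manuals and about 20 hours of training | 6.3.3, 6.2 | Described as training to conduct the interventions; no rule for other groups is stated |
| End-of-session checklist | 6.3.3 | No; study sessions only |
| Audiotaping | 6.3.3 | No; intervention sessions only |
| Fidelity questionnaire / exposure checklist | 6.3.3, 8.5 | No; records exposure and its source afterwards |
| Instruction on workshop-unique material | 7.2 | No; individual sessions only |

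Section 7.1 says it would be unfeasible to prevent HIV risk discussions in treatment. That concerns general discussion and treats group and individual settings alike. It therefore does not explain why 7.2 restricts workshop-unique material in one setting and is silent on the other.

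**Step 2: reproduce the protocol's sample size.** Inputs from section 11.3: effect size 0.29, intracluster correlation 0.01, cohort size I = 8, type I error 0.05, power 80%.

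m = 2 × (1.96 + 0.84)² × {1 + 7 × 0.01} / (8 × 0.29²) = 16.7776 / 0.6728 = 24.9, rounded up to 25 cohorts per condition. That is 25 × 8 = 200 men per condition and 400 in all, as stated. The calculation is not in dispute.

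**Step 3: illustrate dilution.** The documents give no contamination rate, so c is an assumption. Suppose a share c of control men gain the whole REMAS benefit. The standardized difference becomes 0.29(1 − c), and

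power = Φ( 0.29(1 − c) / √(2 × 1.07 / n) − 1.96 ),

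where 1.07 is the protocol's design effect and n is evaluable men per arm. The planned 560 with the protocol's 10% attrition gives n = 560 × 0.9 / 2 = 252.

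For example, at n = 252, √(2.14 / 252) = 0.0922. With c = 0, 0.29 / 0.0922 − 1.96 ≈ 1.19 and Φ ≈ 0.88.

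| c | Difference | Power, n = 200 | Power, n = 252 |
|---|---|---|---|
| 0% | 0.290 | 80% | 88% |
| 5% | 0.2755 | 76% | 85% |
| 10% | 0.261 | 71% | 81% |
| 20% | 0.232 | 61% | 71% |

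The n = 252 column matches planned enrolment; n = 200 is the stated minimum. If exposed men gained only half the benefit, 10% exposed would count as c = 5%, and power at n = 252 would be 85%. With the protocol's alternative intracluster correlation of 0.02, n = 252 and c = 10% give 78%.

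**The case against.** Much of the case on the other side stands.

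- **Silence is not permission.** A reader might infer that 7.2 allows a therapist to use REMAS exercises in an ordinary clinic group. It authorises nothing of the kind, and 6.3.3 treats such delivery as contamination. The training content and manuals are not at hand and may address it. What can be said is that the written instruction is narrower than the written concern.
- **The routes are not ranked.** Section 6.3.3 joins them with a simple alternative and calls the matter a possibility. The protocol does not say they matter equally, nor that study therapists will lead groups attended by control men. Group experience is only a hiring priority, and outside hires are possible.
- **Section 9.2.1 is not a separate error.** Its list of routes leaves out study therapists' other groups and mentions "substance abuse counselors not associated with the study" among outside sources. A reader might see an omission to correct, but those outside sources are given as examples and the section sends the reader to 6.3.3, where the route is named.
- **The power figures lean toward the worst case.** They credit exposed men with the full effect of a five-session workshop. Fragments heard in a clinic group would probably do less, and the control session already covers condom demonstration, barriers and healthy options.
- **Contamination was weighed openly.** Separate therapists were rejected with reasons, and exposure and its source are measured.

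None of this supplies a restraint on the group route or a reason for leaving it out.

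**Conclusion.** The mismatch between 6.3.3 and 7.2 is real: one of two therapist routes that the protocol names outside study sessions has no written restraint. It could bias the primary comparison toward no effect. Whether it would, and by how much, cannot be determined from the document.

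A reader might infer that the REMAS effect will be diluted or that the trial is underpowered. Neither follows. The illustration rests on an assumed share of control men receiving full benefit, on the protocol's effect size, and on its intracluster correlation of 0.01. Under those assumptions planned enrolment still gives about 81% power at 10% full contamination and falls to 71% at 20%. Nothing in the protocol supports any particular rate.

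This is a modest gap. It is worth closing because the rule already exists for one setting, and exposure cannot be undone once it has occurred.

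**What to change.** Reconcile section 7.2 with section 6.3.3. Make the instruction on workshop-unique material cover both individual sessions and any other group sessions that the study therapists lead during the trial, and include it in the existing training. If groups were left out on purpose, state why. Section 9.2.1 needs no change, and the exposure checklist already records the source of exposure, so no new form is needed.

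The cost is a few words in 7.2 and a line in the training, with no added visits, staff or participants. The downside is small: the trained counselors hold back workshop-unique material in their other groups while the trial runs. The change would reduce this route without removing contamination through REMAS participants or outside sources. Because ordinary groups are not taped, compliance would show only indirectly, through the exposure checklist. The wording should be settled before therapists are trained.

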## **8.0. MEASUREMENTS, EVALUATIONS, AND ANALYTICAL METHODS**

Assessments are conducted at five time points: 1) screening for study enrollment, 2) baseline assessment, 3) post intervention assessment, 4) three month follow up, 5) six month follow up. Measurement tools are described in the section that follows. In Table 3, at the end of the section, the schedule for instrument administration is provided. The post intervention assessment is limited to the measures where it is hypothesized the intervention may have an immediate measurable effect. Participants will be informed and assured that data collected from research assessments will not be shared with treatment staff. Prior research has indicated substance abusers are more likely to self disclose substance use behaviors when there are not legal or clinical contingencies tied to their self report.

A major consideration in planning treatment outcome research involves formulation of an effective plan to ensure follow-up data are obtained. To encourage participation in follow-up, the length of each visit has been kept relatively short. Participants will be paid in cash or vouchers for completion of follow-up assessments. Reasonable and non-coercive reimbursement sums will be determined on a site-by-site basis. It is anticipated that follow up rates for participants while they are still in treatment will be extremely high. Participants who have left the area will be interviewed by phone. A paper/pencil version of the Sexual Behavior Inventory (usually administered via ACASI) will be created so that we can collect data on participants who have left the area or are otherwise unable to be interviewed in person. All participants will complete a locator sheet that identifies stable individuals who are likely to know of the participants' whereabouts in the future. In a previous treatment outcome study conducted in a methadone clinic by the lead investigator the six month follow up completion rate was 91% using similar methods (Calsyn et al. 1994). To obtain a follow up estimate for the ODF sample we turned to the NIDA Collaborative Cocaine Treatment Study where 85.2% of participants completed the 5 or 6 month follow up.

### **8.1 Informed Consent**

Sample consent forms for obtaining written informed consent are provided in the appendix. Consent procedures are described in section 5.3.

### **8.2 Inclusion/Exclusion Criteria Review**

#### **8.2.1. Screening Assessment**

Several assessment instruments from the Common Assessment Battery will be used in the screening phase of this protocol. Participants will be paid in cash or vouchers for completion of the screening assessment. Reasonable and non-coercive reimbursement sums will be determined on a site-by-site basis. The screening assessment will not be audiotaped.

**CTN Demographic Form.** Age, gender, ethnicity, and drug use history are collected.

**Mini-Mental Status Exam (MMSE).** The MMSE (Folstein, Folstein & McHugh, 1975; Cockrell & Folstein, 1988) will be used to identify potential participants who are too cognitively impaired to engage in the study. Individuals with scores less than 25 will be excluded from study (Crum, Anthony, Bassett & Folstein, 1993). MMSE has the advantage of: 1) being widely used in research protocols for this purpose, 2) is relatively easy to administer and score; 3) is relatively short; 4) and has a very low ceiling so that only the most grossly cognitively impaired individuals will be excluded. This instrument will only be administered at the time of screening.

**Risk Behavior Survey.** The RBS is part of the common assessment battery. It is a brief interview assessing involvement in HIV risk behaviors of injection drug use and sexual behavior. Most of the questions assess involvement in risk behaviors for the prior 30 days. Sexual behavior questions will be repeated for the prior six months. If the client indicates no unprotected vaginal or anal sex in the prior six months he will be ineligible to participate in the study.

**Basic Data and Locator Questionnaire.** Locator information, including home address and phone number, will be collected and kept confidential in the participant's record. Data collected on this form will be used to contact the participant for assessment and follow-up and in emergencies. Participants will be asked to provide locator information including their residential street address and a working telephone number, or an address of a relative if they are homeless, as well as the address and telephone number of a non-drug abusing relative or friend who can reach the participant in emergencies.

Participants excluded from the study during the screening assessment will not be informed of the reason for exclusion, so as to not bias screening assessments of other potential participants with whom they may come in contact. Excluded participants will be told there are several subject characteristics criteria that need to be met before a subject can be enrolled into the study. Unfortunately they did not meet one of these criteria. We do not inform excluded participants of the criterion that was not met so as to limit other potential participants from being able to misrepresent themselves if they did not meet similar criteria. With the exception of the RBS injection risk questions, the screening instruments will only be administered at the time of screening.

### **8.3 Baseline and Follow up Assessments**

Participants will be paid in cash or vouchers for completion of the baseline and follow-up assessments. Reasonable and non-coercive reimbursement sums will be determined on a site-by-site basis. Participants will be tracked for follow up interviews. To the degree that it is feasible at a particular site, participants who become incarcerated during the course of the study period will also be tracked and contacted for follow-up interviews. The protocol specific assessments within the Baseline Assessment (not the Common Assessment Battery or ACASI administered SERBAS) will be audiotaped. The following CAB instruments and protocol specific instruments will be used as part of the baseline and follow up assessments.

### **8.3.1. Composite International Diagnostic Interview (CIDI)**

The substance abuse subsections from the Composite International Diagnostic Interview, version 2.1 (CIDI-2.1) will be used to determine whether potential participants meet DSM-IV criteria for substance abuse or dependence. The results of this interview are recorded on the Substance Use Diagnosis CRF. This is administered at the baseline only.

### **8.3.2. Addiction Severity Index-Lite**

The ASI is a standardized, multidimensional, semi-structured, comprehensive clinical interview that provides clinical information important for formulating treatment plans as well as problem severity profiles in six domains commonly affected in substance abusers. The domains covered are chemical abuse (alcohol and drug), medical, psychiatric, legal, family/social and employment/support. Composite Scores for each problem domain are derived mathematically. A revised version of the ASI Fifth Edition, 1997 version (ASI-Lite), that includes only those questions used to derive the composite scores along with some demographic information will be administered by a research staff member. The full ASI-Lite will be administered at the baseline assessment. At the 3 and 6 month assessment only the Drug and Alcohol section will be administered.

### **8.3.3. Drug use and drug injection risk behavior assessment**

Drug use and injection practices Items from the Risk Behavior Survey (RBS) will be repeated if the interval between screening and baseline assessment is longer than 30 days. The RBS drug use and injection practice items will be repeated at the 3 and 6 month follow-up visits.

In addition to the CAB measures listed above the following measures will be collected at the baseline and follow up assessments:

### **8.3.4. Sexual and sexual risk behavior assessment**

Items were selected or adapted from the SADAR (Sex and Drug Abuse Relationship Interview; Calsyn et al 2000) and the SERBAS (Sexual Risk Behavior Assessment Schedule; Meyer-Bahlburg et al., 1991; Sohler et al., 2000). Behaviors include: 1) absolute frequency of vaginal intercourse and relative frequency of unprotected vaginal intercourse by (main versus casual) partner type; 2) number, gender, and HIV serostatus of partners; 3) relative frequency of drug (including alcohol) use with sex. The number of unprotected vaginal and anal intercourse acts, which serves as the primary outcome measure, will be derived from two items for the previous 90 days included in this instrument. This is the same primary outcome measure being used in CTN Protocol 0019 (Safe Sex for Women). The items from the SERBAS and the SADAR will be administered using the audio computer-assisted self-interviewing (ACASI) method. Metzger et al. (2000) and Gross et al. (2000) have shown respondents to be more self-disclosive regarding participation in high risk behaviors with ACASI compared to in person, face-to-face interviews. This method lessens the impact of possible social desirability distortions on the self reporting of involvement in risk behaviors.

At the post intervention assessment only the items related to the most recent sexual event will be asked since the time frame being covered is since the intervention started, and not the past 90 days as will be the case for baseline and the 3 and 6 month follow up assessments.

In addition to self report of risky sexual behavior, it would be possible, although difficult from a CTP feasibility standpoint, to obtain a biological marker of risky sex behavior such as evidence of a new sexually transmitted infection (STI). The protocol development team considered this methodology, but rejected it for the following reasons. In PL the self report of the frequency of unprotected vaginal and anal intercourse was consistent with STI rates in the sample and there was a significant difference in gonorrhea rates at follow up between men in the control and experimental intervention at  $p=.03$  (NMHPTG, 1998). The PL investigators were able to demonstrate this relationship because they powered the study to detect such finding by having a sample size three times as large as proposed in this protocol. In a subsequent analysis of PL data Pinkerton et al., (2002) demonstrated that the self-report of unprotected vaginal and anal sex was the best behavioral predictor of HIV infection. The six-month incidence rates of STI in this population are not high enough to be useful without a very large sample size, and they generate many false negatives. Most people engaging in risky behavior will not become infected during the six-month follow up period. Thus the data will only inform us about the few people who deny risky behavior, but then become infected. Although this information might be of some marginal use, it comes at too high a price. The most useful STI would probably be Chlamydia. However, in two studies with drug abusers the prevalence rates were only 6.8 and 3.7% (Lu-Yu Hwang et al. 2000; DeHovitz et al. 1994); incidence rates will be much lower. The feasibility difficulties arise because to get this information we would need to test everyone by collecting a UA sample (collection & testing costs). Participants would need to be given feedback on the results (counseling costs), and infected individuals would need to be treated and retested (treatment, additional collection and testing costs).

